The Pathway Platform consists of a mobile app for patients and a care team interface that can be accessed through Epic. We intend to enroll 200 patients who meet the eligibility criteria for this study and agree to download the Pathway Platform. An additional 200 patients will be identified from the same participating clinics to form the pre-implementation cohort. These are patients who visited the participating clinics at least 6 months prior to study implementation; they will not be actively enrolled into the study and their data will be collected retrospectively through chart reviews and electronic data pulls.

LIST OF ABBREVIATIONS

AE	Adverse Event
APA	American Psychiatric Association
APPS	Mobile Health Applications
ASEX	Arizona Sexual Experience Scale
CCM	Collaborative Care Model
DSST	Digit Symbol Substitution Test
ED	Emergency Department
EMR	Electronic Medical Record
GAD	Generalized Anxiety Disorder
GAS	Goal Attainment Scale
GAD	Generalized Anxiety Disorder
IRB	Institutional Review Board
IQR	Interquartile Range
MBC	Measurement Based Care
MDD	Major Depressive Disorder
PAM-13	Patient Activation Measure
PDQ-D5	Perceived Deficits Questionnaire- Depression
PHQ-2	Patient Health Questionnaire-2
PHQ-9	Patient Health Questionnaire Depression
PROMIS	Patient-Reported Outcomes Measurement Information System
PSD-6	PROMIS Sleep Disturbance 6a
PTSD	Post-Traumatic Stress Disorder
SAE	Serious Adverse Event
SD	Standard Deviation
SDM	Shared-Decision Making Model
SSR	Special Situation Report
WSAS	Work and Social Adjustment Scale
WHO-5	World Heart Organization- Five Well Being Index

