4.1 Inclusion

1. Adult aged 18 and above

2. Diagnosis with major depressive disorder or reference to “clinical depression” in patient charts. See **Appendix 1** for ICD codes for major depressive disorders
3. Recently prescribed monotherapy antidepressant medication (defined as new start, medication switch, or dose change in the past 3 months (**Appendix 2**).
4. Patients with inadequate response or tolerability concerns determined based on A PHQ-2 score of 3 or greater, or a PHQ-2 <3 with a PHQ-9 score of 5 or greater recorded in medical records in the past 6 weeks or during screening,
5. Able and willing to provide informed consent
6. Able to use the Pathway Platform based on clinician’s judgment, e.g. owns an iPhone version 5 or later or smartphones with Android operating systems, have an active data plan or regular WiFi access.

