8.2 Sample size and randomization

The primary outcome for this study is PHQ-9 utilization. Assuming 75% PHQ-9 utilization prior to implementation of the Pathway Platform and 90% PHQ-9 utilization after implementation of the Pathway Platform, we will need 100 patients per group, for a total of 200 patients, assuming 80% power and a 2-sided alpha of 0.05 using Pearson chi square test for two independent proportions. To allow for subgroup analyses the sample will include 200 patients per group, for a total of 400 patients; 200 patients will comprise the “post-implementation” cohort and 200 will comprise the “pre-implementation” cohort. **Table 2** presents additional sample size calculations based on different assumptions of PHQ-9 utilization.

Table 2: Sample size calculations based on different assumptions of PHQ-9 utilization, alpha = 0.05, Power = 80%.
--

PHQ-9 utilization pre-implementation	PHQ-9 in Pathway post-implementation	N patients per group
75%	80%	1,094 per group
75%	90%	100 per group
75%	95%	49 per group
50%	65%	170 per group
50%	80%	30 per group
50%	90%	20 per group

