8.3.2 Secondary outcome

Process outcomes: The following secondary process outcomes will be compared between patients attending clinics pre- and post- implementation of the Pathway Platform.

- Measurement- based care: The proportion of patients reflecting measurement-based care informed MDD treatment adjustments in their charts, defined as at least one dose change, medication switch, or add on medication during the study period. The frequency and types of treatment adjustments will also be explored.
- Shared- decision making: The proportion of patients reflecting shared-decision making, using the OPTION12 Tool framework.²⁶ The tool will be modified by adding a thirteenth domain inquiring about goal setting (Asking the patient or caregiver about goals of treatment). The frequency and domains of shared-decision making will also be explored in a manual chart review and a variable added to assess if the clinician documented asking the patient about their goals of treatment.
- Referrals to behavioral health: The proportion of patients with at least one referral will be compared. The frequency and types of referrals will also be explored.
- Follow-up after hospitalization for mental illness: The proportion of hospitalized adults who receive follow-up within 7 days of discharge and within 30 days of discharge.
- Follow-up after emergency department visit for mental illness: The proportion of adults

who receive follow-up within 7 days of discharge and within 30 days of ED visit.

- Healthcare resource utilization: Number and costs associated with hospital admission, length of stay, emergency room admissions, and encounters with outpatient clinics. Costs will be calculated using USA national average costs for inpatient and outpatient visits or using an average Advocate Health Care system cost.

Patient clinical outcomes: The following outcomes will be compared between patients attending clinics pre- and post- implementation of the Pathway Platform, keeping in mind that the number of patients with these measures in the pre- implementation patient group will be limited:

- MDD remission: The proportion of patients with PHQ-9 ≤ 5 at the end of the study period. The last measurement available during the study period will be used to calculate remission.
- MDD response: The proportion of patients with a 50% or greater reduction in PHQ-9 scores. The first and last scores available during the study period will be used to calculate response.

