8.3.3 Exploratory outcomes

Patient clinical and reported outcomes:

- The following patient reported outcomes will be collected in the Pathway Platform throughout the study. The difference in scores between the baseline measure, 6-months, and end of the study will be compared. This will be restricted to patients who completed these scales at these two-time points. To be inclusive of all patients, additional analyses will be conducted to compare first and last scores available:
 - PHQ-9
 - WHO-5
 - PDQ-D5

- The following patient reported outcomes will be collected in the Pathway Platform and described at 6-months and end of the study:
 - Antidepressant Medication adherence
 - Antidepressant Medication dose adjustment and switches
 - Side effects
 - Depression remission
 - Depression response
 - Goal attainment
- Patient reported outcomes (PAM-13, CollaboRATE and WSAS) will also be explored at 6 months and end of the study.

Pathway Platform and report utilization: Pathway Platform analytics will be explored to understand patient adherence to the platform which includes frequency of logging into the Pathway Platform and frequency of completing each of the Pathway Platform functionalities. Care-team utilization of Pathway Platform reports will also be explored, including describing type of care team members who viewed the Pathway Platform reports as well as frequency of viewing the reports.

Education utilization: Frequency of viewing material in the resource education center will be described by patient and by care-team members. Commonly viewed educational material will be highlighted.

Subgroup analysis: primary, secondary, and exploratory outcomes will be compared across a number of patient demographic and clinical characteristics, including PHQ-9 severity at baseline, comorbidities (see appendix 3 for comorbid conditions and ICD codes), app utilization by patients, and EMR report utilization by providers. Additional subgroup analysis will be conducted by type of care model at the site level (e.g. collaborative care vs. non collaborative care sites).

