8.4 Data analysis

For primary and secondary hypothesis testing, process measures, patient clinical outcomes, and health care resource utilization will be compared pre- and post- implementation of the Pathway Platform.

Additional patient reported outcomes will be compared among patients using the Pathway Platform only at baseline and end of study. For pre-implementation, outcomes will be assessed among patients who visited one of the study clinics at least once over the pre-implementation study period and were eligible to use the Pathway Platform, if it had been available. For the post-implementation period, the Pathway Platform will be the data source for paired t-test analysis, assessing change in continuous variables including PHQ-9 scores. Categorical outcomes will be presented as proportions and compared using Pearson Chi2 test. Continuous outcomes will be assessed for normality and presented as means and standard deviations (SD) or medians and interquartile ranges (IQR); continuous outcomes will be compared using Student's t test for independent groups. Two-tailed tests using a significance threshold of $p < 0.05$ will be used for all tests.

Exploratory outcomes: will be described among patients attending the pathway platform clinics only and will be compared between baseline, 6-month and extended follow up. Change in these outcomes overtime, including utilization analytics will also be explored. Categorical outcomes will be presented as proportions and compared using McNemars' test. Continuous outcomes will be assessed for normality and presented as means and standard deviations (SD) or medians and interquartile ranges (IQR); continuous outcomes will be compared using Student's Paired t test for single group comparison. Two-tailed tests using a significance threshold of $p < 0.05$ will be used for all tests. Goal attainment will be summarized by proportion of patients who achieve their identified goals based on the set time bound duration of the goal (i.e., GAS Score ≥ 50).^{29,30} The goal attainment scale adapted for depression yields a norm-based score (standardized to a mean of 50, SD of 10) at baseline and at the end of the time bound goal; the change from score from baseline will also be summarized.

System level performance: Process outcomes will be evaluated at the system level (all primary

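### Remission is compared between two non-randomised cohorts with no adjustment for entry PHQ-9, so a difference in starting severity can look like a Platform effect or hide one

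*Combined protocol and SAP*

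**What the plan says.** - **Outcome.** Section 8.3.2 lists remission among the patient clinical outcomes compared between cohorts: "The proportion of patients with PHQ-9 ≤ 5 at the end of the study period". The last available score in the period is used. Response is a fall of at least half from the first to the last available score. The same section warns that few pre-implementation patients may have these measures.
- **Test.** Section 8.4 places patient clinical outcomes under primary and secondary hypothesis testing and gives one between-cohort method for them: "Categorical outcomes will be presented as proportions and compared using Pearson Chi2 test". No covariate, stratified test, regression or propensity method is named for any cohort comparison.
- **Cohorts.** Section 8.2: "200 patients will comprise the “post-implementation” cohort and 200 will comprise the “pre-implementation” cohort". Post patients consent and use the app. Of the pre patients, the opening summary (Sample Size and Population) says "they will not be actively enrolled into the study and their data will be collected retrospectively". Section 3.2 allows group-level matching on age and sex, conditional on patient numbers.
- **Entry severity.** Section 4.1 admits patients on "A PHQ-2 score of 3 or greater, or a PHQ-2 <3 with a PHQ-9 score of 5 or greater". Section 3.2 applies the inclusion criteria to the pre cohort as well.
- **Use of baseline severity.** Section 8.3.3 names "clinical characteristics, including PHQ-9 severity at baseline" as a subgroup factor, under exploratory outcomes.

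**The concern.** A fixed cutoff on the final score is easier to reach from a lower start. If the two cohorts start at different severity, their remission proportions differ even when the Platform does nothing, and a real effect can be hidden in the same way.

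A difference in start is plausible because the cohorts are formed differently. One consists of patients flagged from clinic schedules who are approached, consent and are judged able to use the app. The other is drawn from past charts. At the boundary the link is direct: a patient may enter with a PHQ-9 of 5 under 4.1 and already satisfy remission under 8.3.2, so the share of such patients in each cohort feeds straight into the comparison.

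Remission is one of the patient outcomes behind the secondary hypothesis in 8.1, which expects greater improvement than under previous practice. The primary outcome, PHQ-9 utilization, is not touched by this point.

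**Working it through.** **1. The plan's own figure.** The documents give no expected rate or sample size for remission. The only sizing is for utilization: "Assuming 75% PHQ-9 utilization prior to implementation of the Pathway Platform and 90% PHQ-9 utilization after implementation", "assuming 80% power and a 2-sided alpha of 0.05 using Pearson chi square test for two independent proportions". With the pooled formula,

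n = [1.960·√(2·0.825·0.175) + 0.842·√(0.75·0.25 + 0.90·0.10)]² / 0.15² = (1.053 + 0.443)² / 0.0225 ≈ 99.5, so 100 per group.

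The stated figure reproduces. It says nothing about remission.

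**2. Size of a spurious remission difference.** All inputs are assumptions: entry PHQ-9 SD 5; six-month PHQ-9 mean 9 and SD 6 in the reference cohort; correlation ρ between entry and final score of 0.4 to 0.6; no Platform effect.

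Slope of final on entry score = ρ·6/5. For an entry gap g, remission = Φ((5.5 − 9 − g·ρ·6/5)/6), where 5.5 is the continuity-corrected cutoff. At g = 0: Φ(−0.583) = 28.0%.

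| Entry gap | ρ = 0.4 | ρ = 0.5 | ρ = 0.6 |
|---|---|---|---|
| 1 point | 25.4% (−2.6) | 24.7% (−3.3) | 24.1% (−3.9) |
| 2 points | 22.9% (−5.1) | 21.7% (−6.3) | 20.5% (−7.5) |
| 3 points | 20.5% (−7.5) | 18.9% (−9.1) | 17.3% (−10.7) |

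**3. Chance of a false p<0.05.** Take ρ = 0.5, the pre cohort at 28.0% and the more severe post cohort with 180 scored. The chance is Φ((d − 1.96·SE₀)/SE₁) plus the small opposite tail, with SE₀ pooled and SE₁ unpooled. For a 2-point gap and 150 pre patients: d = 0.063, SE₀ = 0.0476, SE₁ = 0.0478, giving 0.264 + 0.001 = 0.265.

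| Pre patients scored | 1 point | 2 points | 3 points |
|---|---|---|---|
| 150 | 10.4% | 26.5% | 50.1% |
| 75 | 8.8% | 20.0% | 37.2% |
| 50 | 8.1% | 16.7% | 30.4% |

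Fewer scored patients lower the error rate. The bias in percentage points stays the same.

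**4. A second model, and response.** In a simulation with entry scores restricted to 5–27 (SD 5 before restriction), residual SD 4.5 and a slope of final on entry score of 0.4 to 0.8, an entry gap of about 1.6 points gave a spurious remission difference of 4 to 7 points. A gap of about 2.5 points gave 6 to 11. For response, the same 2.5-point gap gave between −2 and +6 points (less severe minus more severe cohort), the sign depending on the slope.

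**5. Masking.** Assume pre-cohort remission of 50%, 30% and 15% in lower, middle and higher entry severity, and a true gain of 10 points in every stratum after implementation.

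- Pre mix 30/40/30: 0.3·50 + 0.4·30 + 0.3·15 = 31.5%.
- Post mix 30/40/30: 41.5%, crude difference +10.0.
- Post mix 20/40/40: 0.2·60 + 0.4·40 + 0.4·25 = 38.0%, crude +6.5.
- Post mix 15/35/50: 0.15·60 + 0.35·40 + 0.5·25 = 35.5%, crude +4.0.

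Power at 200 per group falls from 55% to 28% to 13%. Standardising on entry severity recovers the 10 points in each case.

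**The case against.** **Shared criteria.** Both cohorts come from the same clinics and meet the same PHQ threshold and the same recent-antidepressant-change criterion. That makes a large gap less likely, and on an SD of 5 gaps of 2 and 3 points are 0.4 and 0.6 SD, which is not small. It stands as a reason for caution about size. It does not equalise severity above the floor.

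**Severity subgroups.** Section 8.3.3 will compare secondary outcomes by baseline PHQ-9 severity, and 8.2 doubled the sample to allow subgroup analyses. A reader might infer that the plan ignores entry severity, and that would be wrong: the subgroups could make an imbalance visible. They still give no severity-adjusted overall cohort estimate, and the chi-square remains the test.

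**Response.** It is tempting to treat remission and response as equally exposed. The definitions do not support that. Response is scaled to the patient's own first score, and step 4 shows a mostly small bias of uncertain sign.

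**A simple adjustment brings its own problems.** This stands, in three parts.
- The entry score could be a chart score before implementation and an app score after it, and a study cited in 2.1 found app scores consistently higher.
- A patient with one score would have the same value as covariate and outcome.
- A category for missing entry PHQ-9 could fall mostly in the pre cohort and nearly coincide with it.

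The fix must deal with each.

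**Conclusion.** The point holds for remission. The plan compares an absolute cutoff between non-randomised, differently formed cohorts without adjusting for a starting score that the study already gathers for many patients.

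The figures rest entirely on the assumed SDs, mean, correlation and numbers scored. They show that a gap of 1 point matters little (about 3 to 4 points of remission) and that 2 to 3 points could matter a good deal (5.1 to 10.7 points).

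A reader might go further and infer that the comparison is biased in the Platform's favour, or that the secondary hypothesis cannot be tested. The documents support neither. They give no entry PHQ-9 distribution, so the gap and its direction are unknown, and the secondary hypothesis also covers provider processes. For response, only a weaker statement is justified: some exposure, direction uncertain.

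**What to change.** In 8.4:

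1. Make the cohort comparison of remission a logistic model with cohort and continuous entry PHQ-9. Report the standardised risk difference with its confidence interval. Keep the chi-square as the unadjusted display.
2. Apply the same model to response as a secondary consistency analysis.
3. Define entry PHQ-9 by the same window in both cohorts. Prefer the clinic chart score that established eligibility over the app's Day 1 score. Because 4.4.2 sends Platform data to the EMR, record the source of each score. Repeat the analysis with the app score as a sensitivity analysis.
4. Limit the adjusted model to patients with an entry PHQ-9 and a separate later score. Report by cohort how many are left out, for PHQ-2-only entry or for a single score. Do not use a missing-score category.
5. Reconcile 4.1 and 8.3.2 on patients who enter at a PHQ-9 of 5.

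The cost is SAP wording, one model per outcome, a sensitivity run, and coding of score source and date from data already planned for collection. The adjusted sample will be smaller, mainly in the pre cohort. Adjustment does not correct for calendar time, for consent to use the app, or for who has a last score, and the report should say so.

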3.1 Performance among participating clinics post-implementation

The Pathway Platform will be implemented in up to 20 primary care sites within the Advocate Aurora Health system and enroll a total of 200 patients for six-month duration. The visit where the patient has been onboarded to the Pathway Platform will be the enrollment visit (Figure 1). During the post- implementation period, data on patient outcomes will be collected through the Pathway Platform. At the end of the study an electronic and manual chart review for patients using the Pathway Platform will be conducted among participating clinics and performance related to measurement-based care, shared decision making and collaborative care, where applicable, will be assessed over the post-implementation period.

3.2 Retrospective Assessment: pre-implementation performance at the clinic level (before Pathway Platform implementation)

To assess Advocate's primary care sites performance pre-implementation, an electronic and manual chart review will be conducted from the same Advocate primary care clinics participating in the implementation study. Patients with a clinic visit at least 6 months prior to implementation (index visit) of the Pathway Platform and meeting the inclusion criteria for enrollment in the study, will be included in this analysis (figure 1). Patient history will be evaluated for three months prior to index visit to confirm eligibility. The goal is to capture patients with a new start, dose adjustment or switch of an antidepressant medication 6 months prior to the implementation index date (three-month inclusion window for patient identification). Six months of patient history will be “retrospectively” collected for this baseline patient cohort to assess the primary outcome, defined as PHQ-9 utilization, and other secondary outcomes outlined in the protocol. This analysis will serve as the comparison control for the primary and secondary outcomes to compare performance at the same clinics pre and post-implementation of the Pathway Platform. Depending on the number of eligible patients identified per site (20 per site), group level matching for age and sex may be conducted. The primary endpoint will be the proportion of patients with at least 2 PHQ-9 scores.

Figure 1: Study schematic

* Primary and secondary outcomes will be evaluated at 6 months, data collected beyond 6 months will be used for exploratory analysis

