4.2 Exclusion

1. Missing PHQ-2/PHQ-9 score in the past 6 weeks and/or unable to perform PHQ-2/PHQ-9 at index visit
2. Diagnosis with bipolar depression, schizophrenia, and/or schizoaffective disorder, (**Appendix 1**).
3. Patient no longer under primary care for depression and has transitioned to a psychiatric care team (i.e., Psychiatrist, Advance Practice Psychiatric Nurse, Psychiatric Nurse Practitioner, Psychiatric Physician Assistant).
4. Lack of functional English literacy (indicated by primary language in EMR).

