5. STUDY PROCEDURES

5.1 Schedule of events

Table 1: Schedule of evaluations

	Pre-electronic and manual chart reviews	Complete education by care team	Screening	Baseline assessment	6 month Assessment	Final assessment		
Study Day/Week:		Day -1	Day 0	Day 1	Day 168 - 172 [^]		Study end	
Visit Windows (Days):	Source		EMR/ patient scheduling	Pathway Platform	Pathway Platform	EMR and Manual Review	Pathway Platform	EMR and Manual Review
Patient electronic screening			X					
Informed consent			X					
Onboarding			X					
Demographic characteristics	X							
Number of PHQ-9 scores documented	X			X	X	X	X	
Treatment adjustments	X			X	X	X	X	
Shared decision making (OPTION-12 and CollaboRATE)	X			X	X	X	X	X
Referral to behavioral health	X					X		X
PHQ-9 scores	X			X			X	
Emergency room visits	X					X		X
Emergency room visits due to mental illness	X					X		X
Hospital admissions	X					X		X
Follow up after emergency room and hospital visits	X					X		X
Hospital admissions due to mental illness	X					X		X
Healthcare resource utilization								
Outpatient visits including phone calls	X					X		X
Outpatient visits including phone calls due to mental illness	X					X		X
Remission and response (using PHQ-9 data)	X				X		X	
PAM 13 ***				X	X			X
CollaboRATE**, ***				X	X			X
WSAS ***				X	X			X
PHQ-9				X	X	X	X	X
WHO-5				X	X			X
PDQ-D5				X	X			X
Medication adherence				X	X			X
Side effects				X	X			X
PSD-6 (only if reporting side effects of sleep problems)				X	X			X
ASEX (only if reporting side effects of sexual problems)				X	X			X
Goal Setting				X				
Goal Attainment					X			X
App analytics				X	X			X
Report analytics				X	X			X
Educational material analytics				X	X			X
In depth interviews (Patients and Clinicians)								X
Adverse Events*	X		X	X	X		X	X
Serious Adverse Events	X		X	X	X		X	X

[^]Day 168 reflects end of initial 24 week study period in which the final set of care questionnaires are available for completion (PHQ-9, WHO-5 and PDQ-D5), these expire within 3 days. Day 172; The off-boarding process is available, including the research questions (PAM-13, WSAS,

CollaboRATE), these expire after 30 days.

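### Remission and response use the last available PHQ-9 without requiring that it follow the index score, so the pre/post comparison is mixed with when and how often scores were recorded

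*Combined protocol and SAP*

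**What the plan says.** Section 8.3.2 defines remission as "The proportion of patients with PHQ-9 ≤ 5 at the end of the study period", and the next sentence sets how it is obtained: "The last measurement available during the study period will be used to calculate remission". For response (a fall of at least 50%), "The first and last scores available during the study period will be used to calculate response". The same section warns that "the number of patients with these measures in the pre- implementation patient group will be limited", but gives no rule for patients with one score or none.

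The footnote to Figure 1 fixes the horizon: "Primary and secondary outcomes will be evaluated at 6 months, data collected beyond 6 months will be used for exploratory analysis".

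Entry criterion 4 in section 4.1 accepts "A PHQ-2 score of 3 or greater, or a PHQ-2 <3 with a PHQ-9 score of 5 or greater recorded in medical records", within the past 6 weeks or at screening. Exclusion 1 in section 4.2 is "Missing PHQ-2/PHQ-9 score in the past 6 weeks and/or unable to perform PHQ-2/PHQ-9 at index visit", so the qualifying score may be taken at the index visit.

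The app prompts post-cohort patients for a PHQ-9 every two weeks (sections 4.4.1 and 6.2), and the Table 1 footnote says that "Day 168 reflects end of initial 24 week study period in which the final set of care questionnaires are available for completion". Pre-cohort data come from retrospective electronic and manual chart review (section 3.2). Section 8.4 compares categorical outcomes between cohorts by Pearson chi-square, without adjustment.

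**The concern.** Remission is named as an end-of-period state but is computed from whatever score came last. Nothing requires that score to be later than the index score or sets a minimum gap. One PHQ-9 taken at the index visit is therefore enough to classify a patient for remission. For response, the same single score would be both first and last and give 0% change; whether that counts as non-response or as not assessable is unstated. If only patients with scores are analysed, remission needs one score and response needs two, so the two outcomes rest on different patients.

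This matters because the platform is meant to change how often the PHQ-9 is recorded; that is the primary outcome. The intervention therefore alters the measurement of these two secondary outcomes, and an unadjusted comparison cannot separate a change in depression from a change in recording.

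There is also an overlap. A patient with PHQ-2 below 3 and PHQ-9 of 5 meets the entry criterion and already meets the remission definition. The PHQ-2 route has no PHQ-9 floor at all. An unchanged patient can count as remitted.

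Remission and response are the only patient clinical outcomes tested between the cohorts; the progress-note item is descriptive. They carry the depression part of the secondary objective.

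**Working it through.** **The plan's own figure.** Section 8.2 gives no planning figure for remission or response. For the primary outcome, 75% vs 90%, 80% power, two-sided 0.05, pooled proportion 0.825:
n = [1.960·√(2·0.825·0.175) + 0.842·√(0.75·0.25 + 0.90·0.10)]² / 0.15² = 99.5, i.e. 100 per group. The stated figure reproduces. The plan enrols 200 per group.

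**Patients with fewer than two scores.** On those rates, 25% of the pre cohort (50/200) and 10% of the post cohort (20/200). These are planning rates for EMR documentation and may not equal the shares evaluable for remission or response.

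**Illustration 1: entry score used as the last score.** Assumptions not in the documents: true remission p = 0.30 in both cohorts; every patient below two scores has one, taken at entry; a share q of those entry scores is ≤5.
pre = 0.75p + 0.25q; post = 0.90p + 0.10q. False positives are exact rejection probabilities of the chi-square test (no continuity correction) at 200/200.

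| q | pre | post | gap (points) | false positives |
|---|---|---|---|---|
| 0 | 22.5% | 27.0% | +4.5 | 18% |
| 0.1 | 25.0% | 28.0% | +3.0 | 10% |
| 0.2 | 27.5% | 29.0% | +1.5 | 6% |
| 0.3 | 30.0% | 30.0% | 0 | 5% |
| 0.4 | 32.5% | 31.0% | -1.5 | 6% |

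If only half of these patients have that one score and q = 0, the groups are 175/190: 0.225/0.875 = 25.7% vs 0.270/0.950 = 28.4%, a gap of +2.7 points (9%). If none has a score, the gap is 0 (5%).

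**Illustration 2: timing alone.** Assumptions: remission rises linearly to 30% at week 24, post last scores fall at week 24, and 150/180 patients are evaluable.
- Pre last scores at week 20: 0.30·20/24 = 25% vs 30%, a gap of 5 points, about 17% false positives.
- Pre last scores at week 16: 0.30·16/24 = 20% vs 30%, a gap of 10 points, about 55%.

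**Illustration 3: restricting to patients with scores.** Response 40% overall in both cohorts, rate u in unmeasured patients, evaluable shares f: observed = (0.40 - (1-f)u)/f.
- 150/180 (f = 0.75, 0.90): u = 0.2 gives 46.7% vs 42.2% (-4.4 points); u = 0.6 gives 33.3% vs 37.8% (+4.4). About 13% false positives.
- An assumed 100/170 (f = 0.50, 0.85), as a strict late window might leave: 60.0% vs 43.5% (-16.5) or 20.0% vs 36.5% (+16.5). About 75% and 83%.
- If missingness is unrelated to outcome, there is no bias and about 5%.

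**Overlap.** If a share s of entrants is ≤5 at index and stays there, with 30% remission in the rest, remission rises by s·(1-0.30): 1.4, 3.5 or 7.0 points for an assumed s of 2%, 5% or 10%, in both cohorts alike.

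**The case against.** The strongest reply is that the sizes come from assumptions. The 18% needs every patient below two scores to have exactly one, at entry, and never ≤5; with 20% to 40% of entry scores ≤5, or with no score at all, the rate is 5% to 6%. The timing figures need an assumed recovery curve. That stands: the documents settle neither the size nor the sign.

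It can also be said that a chart score from up to 6 weeks before the index visit does not naturally fall within the study period. That stands in part. The text does not say whether such a score counts, so the gap is clear only for a score taken at the index visit.

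Table 1, as extracted, places remission and response for the post cohort under platform columns, so the 90% EMR rate may not be that cohort's evaluable share. The layout may be broken, but the caution is fair.

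Three stronger readings might be inferred and are not supported:
- That the rule favours the platform. Illustrations 1 and 3 give gaps of either sign.
- That post patients are followed for remission to the end of the study while pre patients get six months. Section 5.2 does collect post-cohort data to study end, but the Figure 1 footnote makes anything beyond 6 months exploratory.
- That the overlap at a PHQ-9 of 5 creates a pre/post difference. Both cohorts share it, and on the PHQ-9 route it is a single value.

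The plan does warn of limited pre-cohort data and plans subgroups by baseline PHQ-9 severity (section 8.3.3). Neither deals with score timing or single scores.

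**Conclusion.** The point holds and should be corrected before chart extraction. As written, section 8.3.2 lets an index-visit PHQ-9 stand as the end-of-period score. It also compares a cohort scored on a schedule with one scored at arbitrary dates, using a test that takes no account of either. A difference, or its absence, could reflect recording and not depression status.

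The size is illustrative. With no true difference, the 75%/90% rates of section 8.2 and 30% true remission, the false gap from entry scores runs from +4.5 to -1.5 points and can be 0. Timing alone can give 5 or 10 points under an assumed linear rise. These figures are not forecasts for this study. The overlap with the entry criterion is a minor, separate inconsistency. The primary outcome is not affected.

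**What to change.** 1. In both cohorts, define the index PHQ-9, stating how a score from the 6-week look-back is treated. Take as outcome the last PHQ-9 strictly after index within the initial 6-month period, using the wording of section 8.3.1. Use one denominator for both outcomes: an index score plus at least one post-index score.
2. Reconcile the remission cutoff in section 8.3.2 with entry criterion 4, and compute remission only in patients whose index PHQ-9 is above the cutoff.
3. For these two outcomes, replace the unadjusted chi-square with a logistic model adjusting for index PHQ-9 and time from index to last score. Report by cohort the distribution of last-score timing and the number not assessable by reason, with best-case and worst-case bounds for those patients.
4. Fix a common late window before extraction and use it as a sensitivity analysis only. As the sole analysis it could enlarge selection bias: in illustration 3 the gap grows from ±4.4 to ±16.5 points at 100/170.

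The cost is wording and minor programming, with no new data collection. Patients who entered on PHQ-2 without an index PHQ-9, and patients with no post-index score, become not assessable; for the retrospective cohort these scores cannot be recovered. Intervals widen: at 40% response the 95% half-width, 1.96·√[0.24·(1/n₁ + 1/n₂)], goes from 9.6 points at 200/200 to 10.6 at 150/180. Unequal measurement is reduced and disclosed, not removed.
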